## 4.6 Analysis of Safety

### 4.6.1 Adverse Events and Serious Adverse Events

Adverse events (AEs) will be captured following the lactic acid stinging test procedure.

All adverse events (AEs) will be summarised by primary system organ class and preferred term according to the current version of the MedDRA.

TEAEs are defined as new AEs that occur on or after the date/time of first supervised treatment product use. Events with an onset date/time prior to the first use of treatment product will be considered as non-treatment emergent.

Treatment emergent adverse events (TEAEs) will be summarized by the number and percentage of subjects having any adverse event, an adverse event in each System Organ Class, and each individual adverse event. All TEAEs will also be tabulated by severity. Treatment-emergent AEs suspected of a relationship to study product will be presented in a similar manner. For treatment-related AEs, these will also be presented by severity.

Deaths occurring during treatment (if any) will be listed by treatment, including the date and study day of death, and the principal cause of death. Serious adverse events leading to discontinuation will be listed. All AEs will be listed.

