7. SAFETY ASSESSMENTS

7.1. Definitions of an Adverse Event and Serious Adverse Event

7.1.1. Adverse Events

The investigator or site staff will be responsible for detecting, documenting and reporting events that meet the definition of an AE or SAE.

Adverse Event Definition:

- a) An AE is any untoward medical occurrence in a patient or clinical investigation subject, temporally associated with the use of an investigational product (or the lactic acid stinging test procedure), whether or not considered related to the investigational product (or the lactic acid stinging test procedure).
- b) NOTE: An AE can therefore be any unfavorable and unintended sign (including an abnormal laboratory finding), symptom, or disease (new or exacerbated) temporally associated with the use of an investigational product (or the lactic acid stinging test

 GlaxoSmithKline	Document Name	Clinical Protocol 207782		
	Type	Version	Document Identifier	Effective Date
	eldo_clinical_doc	2.0; Most-Recent; Effective; CURRENT	090032d580d48db0	26-May-2017 05:53:15
	Reason For Issue	Auto Issue		

procedure).

Events meeting AE definition include:

- a) Any abnormal laboratory test results (if applicable) or other safety assessments, including those that worsen from baseline, and felt to be clinically significant in the medical and scientific judgment of the investigator.
- b) Exacerbation of a chronic or intermittent pre-existing condition including either an increase in frequency and/or intensity of the condition.
- c) New condition(s) detected or diagnosed after study product administration even though it may have been present prior to the start of the study.
- d) Signs, symptoms, or the clinical sequelae of a suspected interaction.
- e) Signs, symptoms, or the clinical sequelae of a suspected overdose of either study product or a concomitant medication (overdose per se will not be reported as an AE/SAE).

Events NOT meeting definition of an AE include:

- a) Any clinically significant abnormal laboratory findings (if applicable) or other abnormal safety assessments which are associated with the underlying disease, unless judged by the investigator to be more severe than expected for the subject's condition.
- b) The disease/disorder/ condition being studied or expected progression, signs, or symptoms of the disease/disorder being studied, unless more severe than expected for the subject's condition.

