**Attachment 1: List of Data Displays****7 List of Tables, Figures and Listings**

In all outputs, the treatment labels and order for presentation in tables and listings is:

- 1) Micellar Cleanser
- 2) Micellar Foaming Cleanser

Table No.	Table Title (including population)	Template
14.1.1	Subject Disposition	Section 6
14.1.2.1	Demographic Characteristics – Safety Population	Section 6
14.1.2.2	Demographic Characteristics – Intent To Treat Population	Table 14.1.2.1
14.2.1.1	Frequency of Combined Dermatologist and Ophthalmologist Score – Intent To Treat Population	Section 6
14.2.1.2	Frequency of Combined Dermatologist and Ophthalmologist Score by Strata – Intent To Treat Population	Table 14.2.1.1
14.2.2.1	Frequency of Combined Dermatologist and Ophthalmologist Score (Modified) – Intent To Treat Population	Table 14.2.1.1
14.2.2.2	Frequency of Combined Dermatologist and Ophthalmologist Score (Modified) by Strata – Intent To Treat Population	Table 14.2.1.1
14.2.3.1	Frequency of Combined Dermatologist Score – Intent To Treat Population	Table 14.2.1.1

14.2.3.2	Frequency of Combined Dermatologist Score by Strata – Intent To Treat Population	Table 14.2.1.1
14.2.4.1	Frequency of Combined Ophthalmological Score – Intent To Treat Population	Table 14.2.1.1
14.2.4.2	Frequency of Combined Ophthalmological Score by Strata – Intent To Treat Population	Table 14.2.1.1
14.2.5.1	Frequency of Dermal Response Score – Intent To Treat Population	Section 6
14.2.5.2	Frequency of Dermal Response Score by Strata – Intent To Treat Population	Table 14.2.5.1
14.2.6.1	Frequency of Conjunctiva Involvement Score – Intent To Treat Population	Section 6
14.2.6.2	Frequency of Conjunctiva Involvement Score by Strata – Intent To Treat Population	Table 14.2.6.1
14.2.7.1	Frequency of Lacrimal Intensity Score – Intent To Treat Population	Table 14.2.5.1
14.2.7.2	Frequency of Lacrimal Intensity Score by Strata – Intent To Treat Population	Table 14.2.5.1
14.2.8.1	Frequency of Subject Assessment Scores for Eyes - Intent to Treat Population	Section 6
14.2.8.2	Frequency of Subject Assessment Combined Score for Eyes - Intent to Treat Population	Section 6
14.2.9.1	Frequency of Subject Assessment Scores for Face - Intent to Treat Population	Table 14.2.8.1
14.2.9.2	Frequency of Subject Assessment Combined Score for Face - Intent to Treat Population	Table 14.2.8.2
14.3.1.1	Treatment Emergent Adverse Events by System Organ Class and Preferred Term – Safety Population	Section 6

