14.3.1.2	Treatment Emergent Adverse Events by System Organ Class, Preferred Term and Severity – Safety Population	Section 6
14.3.1.3	Treatment Emergent Treatment-Related Adverse Events by System Organ Class and Preferred Term – Safety Population	Table 14.3.1.1
14.3.1.4	Treatment Emergent Treatment-Related Adverse Events by System Organ Class, Preferred Term and Severity – Safety Population	Table 14.3.1.2

Listing No.	Listing Title (including population)	Template
14.3.2.1	Deaths – All Randomized Subjects	16.2.7.1
14.3.2.2	Serious Adverse Events leading to Discontinuation – All Randomized Subjects	16.2.7.1
16.1.7	Randomization information – All Randomized Subjects	Appendix 8
16.2.1.1	Subject Disposition – All Screened Subjects	Appendix 8
16.2.2	Individual Subjects Protocol Violation – All Randomized Subjects	Appendix 8
16.2.3.1	Exclusions from Analysis Populations – All Randomized Subjects	Appendix 8
16.2.4.1	Demographic Characteristics – All Randomized Subjects	Appendix 8
16.2.4.2	Medical History – All Randomized Subjects	Appendix 8
16.2.6.1	Dermatologist and Ophthalmologist Scores – All Randomized Subjects	Appendix 8
16.2.6.2.1	Subject Self-Assessment (Face) – All Randomized Subjects	Appendix 8
16.2.6.2.2	Subject Self-Assessment (Eye) – All Randomized Subjects	Appendix 8
16.2.7.1	All Adverse Events – All Randomized Subjects	Appendix 8
16.2.7.2	All Adverse Events – Non Randomized Subjects	16.2.7.1

Micellar Cleanser

207782

Draft Statistical Reporting and Analysis plan Amendment #1, 14 Aug 2017

---

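### The treatment-emergent definition has no clause for worsening, so an AE that starts between the lactic acid test and first product use and then worsens on product can be left out of all four AE tables

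*SAP*

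**What the plan says.** SAP Amendment 1 tabulates treatment-emergent AEs without defining them. SAP Addendum 1, section 4.6.1, supplies the definition in two sentences: "TEAEs are defined as new AEs that occur on or after the date/time of first supervised treatment product use", and "Events with an onset date/time prior to the first use of treatment product will be considered as non-treatment emergent". Section 1 of the Addendum states that its changes were identified after unblinding, while the study report was being written.

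Protocol 7.1.1 defines an AE more widely. The note to its definition covers signs, symptoms or disease that are either new or made worse. Its list of qualifying events includes "Exacerbation of a chronic or intermittent pre-existing condition including either an increase in frequency and/or intensity of the condition". Protocol 7.2 starts AE collection after the stinging test and ends it 5 days after the last product use.

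The list of displays in SAP Amendment 1, section 7, has four AE tables:

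- 14.3.1.1: "Treatment Emergent Adverse Events by System Organ Class and Preferred Term – Safety Population"
- 14.3.1.2: "Treatment Emergent Adverse Events by System Organ Class, Preferred Term and Severity – Safety Population"
- 14.3.1.3: "Treatment Emergent Treatment-Related Adverse Events by System Organ Class and Preferred Term – Safety Population"
- 14.3.1.4: the treatment-related table again, split by severity

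Addendum 4.6.1 also promises that "All adverse events (AEs) will be summarised by primary system organ class and preferred term", but no listed table covers all AEs. The complete record for randomized subjects is Listing 16.2.7.1, "All Adverse Events – All Randomized Subjects".

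**The concern.** A treatment-emergent definition should pick up two kinds of event: those that begin on product, and those that were present before and get worse on product. The Addendum's rule covers the first kind. Its second sentence sorts on onset date alone, so an event with a pre-product onset stays outside whatever happens to it later.

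In this trial AE recording opens before product use, after 10% lactic acid has been applied to the face. An AE that begins then, is carried as one record and becomes more severe once the cleanser is used would be absent from the incidence, severity and relatedness tables. With 46 subjects planned per arm, one such subject is visible in a percentage. If the event led to withdrawal, the disposition table could show an adverse-event withdrawal with no matching entry in any AE table.

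**Working it through.** The plan states no figure to reproduce here. The sample size rests on clinical considerations, and there is no target AE rate. The check is mainly of text against text.

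**Inputs**

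- Rule: Addendum 4.6.1, both sentences.
- Start of AE collection: after the stinging test at Visit 1 (Protocol 7.2, item e).
- Gap from Visit 1 to first use at Visit 2: up to 7 days (Protocol, note under the Schedule of Events).
- Planned arm size: 46 randomized, at least 40 completing (Protocol 9.1). The Addendum's safety population is randomized subjects with at least one application, so 46 is the planned denominator.

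**Step 1. Apply the rule to the possible cases.**

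| Case | How it is recorded | Class under Addendum 4.6.1 |
|---|---|---|
| Condition present before AE collection began; worsens on product | Medical history (7.2, item g); the exacerbation is an AE under 7.1.1, with onset after first use | Treatment-emergent |
| AE starts between test and first use; worsens on product; worsening entered as a separate AE | Second record, with onset after first use | Treatment-emergent |
| AE starts between test and first use; worsens on product; kept as one record | One record, with onset before first use | Non-treatment-emergent |
| AE starts between test and first use; does not worsen | One record, with onset before first use | Non-treatment-emergent, correctly |

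Only the third row is misclassified. Neither document says whether the worsening of an AE already on record opens a new record, so the second and third rows are both possible. Protocol 7.5 requires AEs to be followed until they resolve or stabilise and is silent on this. The shell of Listing 16.2.7.1 has start date, end date and intensity, but no date of worsening.

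**Step 2. Count the displays affected.** AE tables restricted to treatment-emergent events: 4 of 4. AE tables that include other events: 0. Listing 16.2.7.1 keeps the event.

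**Step 3. Ask which events can fall in the third row.**

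- Gradable stinging-test responses and responses gradable on Appendix 3 or 4 are not AEs; only unusual reactions are (Protocol 6.1.7, 6.2.5, 6.2.6 and 7.1.1).
- Dermatologist and ophthalmologist scores must be zero at Visit 2 before product use (inclusion criteria 5c and 5d).
- Self-assessed symptoms (Appendix 5) are not among the exclusions from the AE definition, and no zero score is required for them. Non-scored events elsewhere in the body are also open.

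What remains is mainly sensory, unusual or non-scored events that are still present at first use.

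**Step 4. Size one event.** One subject in an arm of 46 is 1/46 = 2.17 percentage points. In an arm of 40 it would be 1/40 = 2.5 points. This is the largest change that one subject can make to a row of the table, and it is zero for the any-event row if she already has another treatment-emergent AE. No rate is given, so the counts below are assumed. The intervals are exact (Clopper-Pearson) 95% intervals.

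| Subjects in the row | Rate | 95% interval |
|---|---|---|
| 0/46 | 0% | 0 to 7.7% |
| 1/46 | 2.2% | 0.1 to 11.5% |
| 2/46 | 4.3% | 0.5 to 14.8% |
| 3/46 | 6.5% | 1.4 to 17.9% |

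**The case against.** The strongest reply is that the design nearly closes the case. Ordinary stinging responses are not AEs. A visible facial or eye reaction at Visit 2 should prevent randomization. Irritation that can be graded on Appendix 3 or 4 goes to the primary endpoint and not to the AE tables under any definition, and burning, itching, stinging, redness and dryness are also collected by self-assessment. An exacerbation can be entered as its own AE and would then count. Listing 16.2.7.1 shows every AE in randomized subjects. The study is non-comparative, has no formal inference, and its success criterion uses no AE data.

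Most of this stands, and it rules out two stronger readings that a reader might take from the rule. The first is that every reaction that begins after the lactic acid test and worsens on the cleanser is removed from the tables. The documents support only that it can be, because they do not say how a worsening is recorded. The second is that the rule discards the irritation signal that the study exists to measure. It does not touch the tolerance scores or the self-assessments. Nor are all 92 planned subjects exposed in any useful sense, given the zero-score requirement.

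The reply does not defend the wording. Post-product scores and self-assessments are taken only at 1 hour and at Visit 3, so a sensory worsening that comes and goes in between is formally captured only as an AE. A listing entry is not a count, and nothing in either document secures the separate record on which the reply depends.

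**Conclusion.** The point holds in a limited form. The definition in Addendum 4.6.1 is narrower than the protocol's AE definition. It misclassifies an AE that starts before first use, is kept as one record and worsens on product. Such an event would be missing from all four AE tables and present in Listing 16.2.7.1.

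The number of these events cannot be derived from the documents and may well be zero. Each affects one row by at most about 2.2 percentage points in an arm of 46. This assumes the planned arm size and that worsening is not given a separate record.

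A reader might also infer from the timing that the definition was chosen to lower the counts. The documents do not support that: the Addendum's Table 1 explains it as matching the definitions already programmed into the outputs. The timing does mean that any reclassification should be reported openly. This is a correction that should be made, and it does not threaten the primary result.

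**What to change.** In Addendum 4.6.1:

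1. Define a treatment-emergent AE as one with onset on or after first supervised use, or one with earlier onset that increases in severity or frequency on or after first use.
2. Keep the earlier-onset sentence, but limit it to events that do not worsen after first use. Deleting it outright is unnecessary.
3. Apply the rule to the AE data already collected, treating a worsening as its own event. Do not add a new data field for the date of worsening, because that would be new data collection after unblinding. Events with onset before and end after first use, or with no end date, can be identified from the existing dates. They bound how many subjects could change class.
4. Report by arm how many subjects change class, and say that the definition was revised after unblinding.
5. Reconcile the sentence promising a summary of all AEs with the list of displays, either by adding that table or by correcting the sentence.

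The cost is a few lines of text, a short review of earlier-onset events in Listing 16.2.7.1, and a small change to the AE flag with a rerun of four tables. Treatment-emergent counts may rise slightly or not at all.

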## 5 Changes to the Statistical Analysis Plan

Any changes from the originally planned statistical analysis specified in the SAP amendment (dated 16-AUG-2017) are outlined in Table 1.

**Table 1 Changes to SAP amendment Defined Analysis Plan**

SAP Analysis Plan Amendment 1	Statistical Analysis Plan Addendum	Rationale for Changes

 
1.1.2 Analysis Population The Safety population includes all subjects from the point of the lactic acid stinging test procedure until completion of the study.
 
	
 
1.1.2 Analysis Population All subjects, for whom the lactic acid stinging test was performed, were randomized and had at least one study treatment application.
 
	
It was originally planned to report all AEs from the point of lactic acid sting test as the subjects would have been applied the acid solution to potential subjects in the study. However this sting test was performed at the screening visit and therefore not everyone who had the sting test performed would have been randomised and received treatment product. Therefore some of the AEs reported after the sting test would not have been classified as treatment emergent. During the programming of the AE TFLs for the CSR, it was assumed all subjects in safety population were randomized and received treatment product, hence any AEs from this safety population definition would have been TEAEs (if started after product use). However the safety population definition applied to the TFLs differed from the planned definition. Once this was identified during the CSR development, the study team decided that the definition of the safety population and TEAE definition applied to the TFLs was the most appropriate. Hence change/clarification to the definitions in this RAP addendum.

 
Section 4.1.1 Subject Disposition
 
	
 
Section 4.1.1 Subject Disposition Additional summary of the number and percentage of subjects who underwent the lactic acid sting test (Table 14.1.1).
 
The derivation for treatment duration has been added in the listing shell in Section 7 as well as in the text under section 4.1.1.
 
	
This information will be useful in the CSR to assess the disposition of subjects between onset of screening and randomisation.
 
 
While reviewing the draft CSR, it had been identified that the calculation of the treatment duration in Listing 16.2.1.1 was not correct (addition of 1 day was not added). No derivation had previously been provided in the RAP amendment.
 

## 7 Template for Table and Listing

Protocol: 207782

Program Run Date: ddmonyyyy

Table 14.1.1  
Subject Disposition

All Screened Subject (N=XXX)

	Micellar Cleanser N (%)	Micellar Foaming Cleanser N (%)	Overall N (%)
TOTAL SUBJECTS SCREENED			XX
TOTAL SUBJECTS UNDERWENT LACTIC ACID STING TEST			XX (XX.XX)
SUBJECTS NOT RANDOMISED			XX
DID NOT MEET STUDY CRITERIA			XX (XX.XX)
ADVERSE EVENT			XX (XX.XX)
LOST TO FOLLOW - UP			XX (XX.XX)
PROTOCOL VIOLATION			XX (XX.XX)
WITHDRAWAL OF CONSENT			XX (XX.XX)
OTHER			XX (XX.XX)
SUBJECTS RANDOMISED	XX	XX	XX
COMPLETED STUDY	XX (XX.XX)	XX (XX.XX)	XX (XX.XX)
DID NOT COMPLETE STUDY	XX (XX.XX)	XX (XX.XX)	XX (XX.XX)
DID NOT MEET STUDY CRITERIA	XX (XX.XX)	XX (XX.XX)	XX (XX.XX)
ADVERSE EVENT	XX (XX.XX)	XX (XX.XX)	XX (XX.XX)
LOST TO FOLLOW - UP	XX (XX.XX)	XX (XX.XX)	XX (XX.XX)
PROTOCOL VIOLATION	XX (XX.XX)	XX (XX.XX)	XX (XX.XX)
WITHDRAWAL OF CONSENT	XX (XX.XX)	XX (XX.XX)	XX (XX.XX)
OTHER	XX (XX.XX)	XX (XX.XX)	XX (XX.XX)
SAFETY POPULATION	XX (XX.XX)	XX (XX.XX)	XX (XX.XX)
ITT POPULATION	XX (XX.XX)	XX (XX.XX)	XX (XX.XX)

PPD

Page X of Y

**Programming note:** For categories under 'Subjects Not Randomized' percentages will be calculated using the number of 'All Screened Subjects' as the denominator. Percentages under the 'Subjects Randomized' categories will be computed using number of subjects randomized as the denominator.

Micellar Cleanser

207782

Final Statistical Reporting and Analysis plan Addendum 1,07Dec 2017

---

PPD

Page x of y

Micellar Cleanser

207782

Final Statistical Reporting and Analysis plan Addendum 1,07Dec 2017

Protocol: 207782

Program Run Date: DDMMYYYY

Listing 16.2.1.1  
Subject Disposition  
All Screened Subjects

Subject	Sex/Age/ Race [1]	Screening date	Treatment Start Date and Time	Date of Completion or withdrawal	Duration of Treatment (Days) [2]	Completed (Yes/No)	Randomized (Yes/No)	Primary Reason for Withdrawal
PPD								

...  
[1] Age in years; Sex: F = Female, M = Male; Race: A = Asian, B = Black or African American, I = American Indian or Alaska Native, H = Native Hawaiian or Other Pacific Islander, W = White, M = Multiple.  
[2] Treatment duration is calculated as [(date of completion or withdrawal minus treatment start date) +1].

PPD

Page x of y

